**Medical University of South Carolina
Protocol**

PI Name: [name]

Study Title: Sensory Stimulation to Enhance Hand Function Post Stroke

NCT02675764

TABLE OF CONTENTS

A. SPECIFIC AIMS	2
B. BACKGROUND AND SIGNIFICANCE	2
C. PRELIMINARY STUDIES	2
D. RESEARCH DESIGN AND METHODS	2
E. PROTECTION OF HUMAN SUBJECTS	3
F. REFERENCES/LITERATURE CITATIONS	7
G. FACILITES AVAILABLE	8

A. SPECIFIC AIMS

The objective of this pilot project is to assess the impact of the novel sensory vibration stimulation technique we have developed in enhancing outcomes of hand therapy as well as the central nervous system responsiveness in chronic stroke survivors. This impact will be assessed in a double-blind stratified randomized controlled trial for stroke survivors. The hypothesis is that improvement in hand function will be greater for the experimental group receiving the wrist subthreshold vibrotactile stimulation during therapy compared with the control group who will wear the device with no vibration (placebo), and that this better improvement in hand function is associated with neurophysiologic measures of central nervous system responsiveness.

B. BACKGROUND AND SIGNIFICANCE

Stroke survivors suffer from persistent hand impairment that diminishes their functional abilities and independence, despite multiple courses of rehabilitation. Sensory stimulation can prime central excitability to increase therapy outcome. Unlike existing methods including transcutaneous electrical nerve stimulation, muscle/tendon vibration, and repetitive transcranial magnetic stimulation (TMS) that require prior exposure to the sensory stimulation as long as 2 hours before each therapy session, we developed a new sensory stimulation technique that has the potential to immediately prime the central sensorimotor system for the hand, using imperceptible vibration applied to the wrist skin. Wearable devices with a vibrating function are low cost and can be easily adopted for rehabilitation purposes to impact a wide range of patients with sensorimotor impairment. In addition, this subthreshold vibrotactile stimulation is unique compared to the traditional stochastic resonance, by stimulating the wrist while improving fingertip tactile sensation. This remote approach exposes the entire hand to receive relevant sensory information and improve the ability to successfully manipulate objects. Despite the potential for clinical benefits and easy adoption for high impact, knowledge about the long-term efficacy of this new sensory stimulation technique and its underlying mechanism is limited. This limitation presents an obstruction to clinical adoption and optimization for efficacy.

C. PRELIMINARY STUDIES

The PI's preliminary studies showed that hand motor scores immediately improved with remote subthreshold (unperceivable) vibrotactile stimulation. Stroke survivors completed the Nine-Hole Peg and Box and Block tests faster with subthreshold (60% of the sensory threshold) vibrotactile stimulation applied to the wrist ($p < .05$) ([name] et al. 2014). The stimulation was generated by Tactor (EAI, Casselberry, FL) placed on the skin using tape. Learning effects were controlled by practice and pseudo-randomizing the stimulation off and on. Improvement in hand motor function with the stimulation was seen not only in stroke survivors but also in healthy adults (Hur et al. 2014).

Preliminary studies also showed that tactile sensation improved with the stimulation. Instantaneously with the stimulation, stroke survivors could detect smaller Semmes-Weinstein monofilaments on the fingertips, indicating improved touch sensation ($p < .01$) (Enders et al. 2013).

D. RESEARCH DESIGN AND METHODS

The hypotheses will be tested in a double-blind stratified randomized controlled trial. Experimental and control groups will be compared for post-therapy changes in hand function. To obtain two comparable groups, stroke subjects will be stratified by their initial hand motor and sensory scores (Fugl-Meyer and Semmes-Weinstein mild vs. moderate). Subjects will be randomly and blindly assigned to either the experimental or the control group. A standardized task-practice therapy focused on dexterous object manipulation and multi-joint upper extremity coordination will be used, since the intervention targets sensory feedback-based motor control. The research therapists at the SC Stroke Recovery Research Center have been trained in its implementation and routinely use this protocol. Each subject will receive therapy two hours/day, 3 days/week for 2 weeks. The duration of 2 weeks is deemed sufficient to result in statistically greater improvement in motor outcome and cortical reorganization (seen using fMRI/TMS) for the experimental compared to the control group. The two groups will receive therapy of equal intensity individually in the same room supervised by the same therapist who is blinded to the group and does not know how the coin-sized device providing the light vibration works. Tactor (EAI, Casselberry, FL) generating light vibration in our preliminary studies will be applied to the wrist. At the beginning of each therapy session, the subject's sensory threshold will be determined and the vibrating intensity will be adjusted to either 60% of the sensory threshold or zero, depending on the group. Blinding to the light vibration stimulation is possible because subjects cannot perceive subthreshold (imperceptible) vibration, thus they do not know whether they are receiving the vibration or not.

Evaluation will be performed before (pre-intervention testing), after (post-intervention testing), and 2 weeks after the therapy (follow up testing). Clinical sensorimotor function of the hand will be assessed using clinical tests, such as the Nine Hole Peg, Action Research Arm, Box and Block test to assess dexterity, as well as the Semmes-Weinstein and Grating Orientation tests to assess sensation. Secondarily, the Stroke Impact Scale and Stroke-Specific Quality of Life Scale will be recorded to assess the potential for the light vibration stimulation to impact patients' self-care abilities. Neurophysiologic evaluation will be performed using the MRI including an anatomical scan, diffusional kurtosis imaging (DKI), and functional MRI (fMRI) during grip, TMS including resting and active motor thresholds and motor evoked potential peak-to-peak amplitudes (all of these variables are routinely used in MUSC TMS evaluation protocols), and EEG evoked potentials and frequency power modulation during grip.

Each subject will visit MUSC for a total of 9 to 12 times over a period of a month. The pre-intervention testing will include screening, clinical hand function assessment, MRI, TMS and EEG. There will be six therapy visits lasting 2 hours each. Post-treatment evaluation will include clinical hand function assessment, MRI, TMS, and EEG after the completion of therapy. Follow up testing will include clinical hand function, TMS, and EEG again 2 weeks after the completion of therapy. Each set of evaluations (pre, post, and follow up testing) can be performed over 2 days to minimize participant fatigue.

Subjects will be paid \$100 total per set of evaluations. For pre- and post-testing, the participant will receive \$25 for each type of evaluation completed (i.e., clinical hand function, MRI, TMS, and EEG) for a total of \$100. For follow-up evaluations, the participant will receive \$33 for clinical hand function, \$33 for TMS, and \$34 EEG for a total of \$100. The participant will receive \$25 per therapy visit for participation in this study. There will be a total of 11 evaluations sessions and 6 therapy visits. If they complete all evaluations and therapy visits, they will receive a total of \$450. If they stop participating in the study, they can keep the payment they have already received, but will not receive any more compensation. If the subject does not complete one of the assessments due to scheduling conflicts or safety risks (see Section 2.b.), the subject will not receive remuneration for that portion of the study. The payment will be in cash, at the end of each visit.

Analysis: Repeated measures ANOVA with post hoc comparisons will be used to determine if each clinical hand function score improves more for the experimental compared with the control group. A significant interaction between time (pre, post, 2 weeks after) and group (experimental/control) will support the hypothesis. Pearson's correlations between the mean change in clinical hand function scores and each of the neurophysiologic measures will be examined to identify relevant neurophysiologic measures for hand function.

Expected Outcomes: Greater recovery of dexterous hand function is expected with the light vibration stimulation (with a significant session×group interaction). This exciting finding will be the first to demonstrate that this unperceivable vibration stimulation at the wrist improves hand therapy outcomes.

E. PROTECTION OF HUMAN SUBJECTS

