1. RISKS TO THE SUBJECTS

a. Human Subjects Involvement and Characteristics

1. The subject will complete safety screening including presence of any metal in the body, history of epilepsy, and concussion.
2. The level of hand and arm movement as well as fingers' touch sensation will be assessed. For movement assessment, the subject will be asked to move the hand and arm in specific ways as best as one can and move objects in different sizes and shapes around the table with the hand as quickly as possible. For sensation assessment, the subject will be asked if s/he can feel a small touch on fingertips.
3. If the subject is eligible for the study, the subject will be randomly assigned to one of two groups. This means that the subject has a 50/50 chance (like flipping a coin) of being in either group. Neither the researchers nor the subject will make the choice of which group to which the subject is assigned. The two groups are Group A (unperceivable wrist vibration group) and Group B (placebo, no wrist vibration group).
4. For both groups, we will ask the subject about the stroke type (ischemic or hemorrhagic) and location as much as the subject knows.

5. For both groups, we will perform four types of evaluations to measure recovery. The assessment of the hand/arm movement ability and finger sensation will serve as evaluation #1 (clinical hand function). Evaluation #1 may take an hour.
6. In addition, the subject will have a Magnetic Resonance Imaging (MRI) exam (evaluation #2). This MRI exam includes an anatomical scan to specify the area of the brain that we will stimulate using transcranial magnetic stimulation (TMS) for the next evaluation, DKI that provides information about the architecture within the cortex relevant to revealing lesion-specific impairment, and fMRI to examine brain networks used during hand grip. For the MRI exam, the subject will lie down on a narrow bed which will then be placed in a tunnel that is 6 feet by 22 inches wide and open at each end. the subject will lie there quietly for about half an hour, during which time the subject will hear a loud noise. The subject may feel warm during this procedure. Evaluation #2 will take approximately an hour.

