9. After completing all evaluations, both groups will receive upper limb therapy 3 times a week for 2 consecutive weeks (for a total of 6 sessions) while wearing a vibrator at the wrist. An off-the-shelf mechanical vibrator in the size of a dime will be used. During therapy, Group A will receive vibration at the wrist at the level that is imperceptible. Group B will receive placebo, also in zero vibration at the wrist, during therapy. Both groups will not feel any vibration at the wrist during therapy, because the vibration is either very small or none. The therapy will focus on object manipulation, dexterous hand movement, and coordinated hand and arm movements.
10. After the last therapy session, all four evaluations (hand clinical function, MRI, TMS, and EEG) will be performed again.
11. Two weeks after the last therapy session, the subject will come to MUSC again to go through the three evaluations again (hand clinical function, TMS, and EEG).

Thirty chronic stroke survivors will be recruited (with 15 in each of the control and experimental groups). The age range will be 21 and older.

The inclusion criteria are mild to moderate impairment in upper extremity function (approximately 30 to 60 on the Fugl-Meyer Upper Extremity without the reflex portion). Exclusion criteria are cognitive dysfunction as evidenced by inability to follow three-step instructions and/or provide consent to participate in the study, stroke<3 months (to avoid interference with acute care), treatment with botox in the affected arm within 3 months of start of study, and age <21. Individuals with MRI contraindications (e.g., metal in the body, claustrophobia, pregnancy) or TMS contraindications (e.g., history of seizure, concussion, pregnancy) may still be considered for the study, but will not complete the contraindicated evaluation. Inclusion is based on clinical assessment, because recovery relates most with initial impairment level, not lesion characteristics.

Targeted/Planned Enrollment Table

Total Planned Enrollment: 30

TARGETED/PLANNED ENROLLMENT: Number of Subjects

Ethnic Category	Sex/Gender		
	Females	Males	Total
Hispanic or Latino	2	2	4
Not Hispanic or Latino	13	13	26
Ethnic Category: Total of All Subjects*	30		
Racial Categories			
American Indian/Alaska Native	0	0	0
Asian	1	1	2
Native Hawaiian or Other Pacific Islander	0	0	0
Black or African American	4	4	8
White	10	10	20
Racial Categories: Total of All Subjects*	15	15	30

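### Randomisation is stratified by Fugl-Meyer and Semmes-Weinstein severity, but the deciding time × group ANOVA leaves both factors out, so power may be lost

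*Combined protocol and SAP*

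**What the plan says.** To make the two arms comparable, Section D (Research Design and Methods) states that "stroke subjects will be stratified by their initial hand motor and sensory scores (Fugl-Meyer and Semmes-Weinstein mild vs. moderate"). Crossed, the two binary factors give four cells. The document does not say how allocation is balanced within them. Section E.1.a says only that "the subject has a 50/50 chance (like flipping a coin) of being in either group", and gives the sample size as 30, "with 15 in each of the control and experimental groups".

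The Analysis paragraph of Section D is the whole statistical plan for efficacy: "Repeated measures ANOVA with post hoc comparisons will be used" for each clinical hand function score, and "A significant interaction between time (pre, post, 2 weeks after) and group (experimental/control) will support the hypothesis". Neither stratification factor appears there, and no other section adds them.

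Two other statements bear on whether the strata predict change:

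- Section E.1.a justifies clinical eligibility criteria on the ground that "recovery relates most with initial impairment level, not lesion characteristics".
- Section D lists Semmes-Weinstein among the outcomes ("as well as the Semmes-Weinstein and Grating Orientation tests to assess sensation"), and Section E.1.a says of the eligibility-stage testing: "The assessment of the hand/arm movement ability and finger sensation will serve as evaluation #1 (clinical hand function").

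**The concern.** When arms are balanced on a factor that predicts the outcome, the treatment estimate becomes more precise. An analysis that omits the factor leaves its variance in the error term, so that precision is not credited: the standard error is overstated and the test rejects too seldom.

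Here the relevant outcome is change, because the time × group interaction compares patterns of change. Having the pre score as one level of time does not adjust for the strata. It removes differences between participants in level, not differences in how much they change. If the strata affect only level, nothing is lost.

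At stake is power. With 15 per arm, each clinical score is judged by this one test.

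**Working it through.** **Inputs from the documents.** N = 30, 15 per arm; two binary strata; three visits; deciding test time × group. The documents give no alpha, effect size, SD, power or R², so there is no planned power figure to reproduce.

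**Assumptions.** Two-sided alpha 0.05; a group difference in change of 0.8 SD at post, kept at follow-up; compound symmetry; each stratum split 50:50; no dropout; R² from 0 to 0.3.

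**Reference power.** With the SD of change set to 1, the within-person error variance is 0.5. The noncentrality is 0.64 × 15 / (3 × 0.5) = 6.4. Power is 0.589 on 2 and 56 df (unadjusted). It is 0.587 on 2 and 52 df (both strata × time terms added, perfect balance). Error df are 2 × (30 − 2) = 56 and 2 × (30 − 4) = 52.

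**Closed form, perfectly balanced strata.** The unadjusted SE is 1/√(1 − R²) times the correct one, and the actual alpha is about 2 × [1 − Φ(1.96/√(1 − R²))]. At R² = 0.1, 0.2, 0.3 the SE ratio is 1.05, 1.12, 1.20 and the actual alpha 3.9, 2.8, 1.9%.

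**Simulation with blocks of 4 within strata** (40,000 trials per cell, Monte Carlo error about 0.25 points):

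| R² | True SD of post − pre difference | Unadjusted SE | Excess | Unadjusted type I | Power, unadjusted → adjusted |
|---|---|---|---|---|---|
| 0 | 0.366 | 0.365 | 0% | 4.8% | 58.8 → 58.2% |
| 0.05 | 0.358 | 0.366 | 2% | 4.6% | 58.9 → 60.2% |
| 0.1 | 0.348 | 0.366 | 5% | 4.2% | 60.0 → 63.2% |
| 0.2 | 0.332 | 0.367 | 11% | 3.2% | 60.9 → 68.2% |
| 0.3 | 0.314 | 0.368 | 17% | 2.4% | 62.6 → 74.8% |

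The adjusted test has type I error of 4.8 to 5.1% throughout. Break-even is at R² of about 0.02 (59.0% either way). Results are nearly the same if only the motor stratum is predictive.

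**Simulation with no balancing within strata** (15:15 overall). The unadjusted test holds 4.8 to 5.1%. Power unadjusted → adjusted at R² = 0, 0.05, 0.1, 0.2, 0.3 is 58.9 → 55.5, 59.4 → 57.8, 60.0 → 60.2, 60.3 → 65.4 and 61.0 → 71.7%. Break-even is near R² = 0.08. The conservatism therefore comes from balancing the strata and then leaving them out.

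**Semmes-Weinstein as an outcome.** If the sensory stratum is taken from the eligibility assessment that doubles as evaluation #1, it is a category of this outcome's own pre score and predicts change through regression to the mean. With equal variances and pre-post correlation ρ, the squared correlation of pre score with change is (1 − ρ)/2. A median split of a normal score retains 2/π of that, so R² = (2/π)(1 − ρ)/2:

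| ρ | R² | Power change, blocks of 4 | Power change, no balancing |
|---|---|---|---|
| 0.9 | 0.03 | about 0 | −3 |
| 0.8 | 0.06 | +1 | −1 |
| 0.7 | 0.10 | +3 | 0 |
| 0.6 | 0.13 | +4 | +1 |
| 0.5 | 0.16 | +5 | +3 |

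**The case against.** The case against is that the planned test is valid, so this is a preference for efficiency in a 30-person pilot. The loss needs two conditions, and the documents establish neither.

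- **Balance within strata.** No blocking or minimisation is stated. Without it the test is not conservative, and adjusting costs power below R² of about 0.08.
- **Strata that predict change.** The sentence on initial impairment sets it against lesion characteristics. It gives no size, does not mention sensation, and says nothing about a mild/moderate split within an already restricted Fugl-Meyer range of about 30 to 60. For Semmes-Weinstein, where R² can be derived, it reaches only 0.16 at ρ = 0.5, and that assumes a median split the protocol does not specify.

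The 0.8 SD effect is also an assumption. At 0.5 SD and R² = 0.2, the gain from adjusting is about 1 to 2 points without balancing and 6 to 7 points with blocks.

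All of this stands as a limit on the size of the benefit. It does not remove the mismatch between design and analysis or change its direction. Nor does it make the remedy unsound: the adjusted test keeps its size, and its cost when the strata predict nothing is small and known.

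**Conclusion.** The concern holds. The protocol stratifies by two factors and then omits both from the only test that decides the hypothesis. The consequence is lost power, conditional on balance within strata and on strata that predict change. With balanced strata the gain from adjusting is small (1 to 3 points) at R² of 0.05 to 0.1 and material only from about 0.2. These sizes rest on assumed R², effect size, covariance structure and block size. The direction does not depend on their particular values. The change is worth making because it is cheap and, at an assumed 0.8 SD effect, power is only about 59%.

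**What to change.** In the Analysis paragraph of Section D, specify the model for each clinical score as: group, time and group × time, plus Fugl-Meyer stratum, Semmes-Weinstein stratum, and the interaction of each stratum with time. The two factors enter additively. The three-visit group × time interaction remains the deciding test. The stratum × time terms are essential, because stratum main effects alone leave that test unchanged.

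Add one sentence on how allocation is balanced within the four strata. The benefit at low R² depends on it: if there is no balancing, adjustment pays only where R² is expected to exceed about 0.08.

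The cost is two sentences, no new data, and 4 error df (56 to 52). If the strata turn out not to predict change, the loss is about 1 point of power with balanced strata and 3 to 4 points without.

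### Imperceptibility is secured only for the wearer at the tested site; the plan does not show that a running device is undetectable to the therapist's hand or the subject's other hand

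*Combined protocol and SAP*

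**What the plan says.** The trial is described as double-blind (Sections A and D). Section D resets the stimulus every session: "At the beginning of each therapy session, the subject's sensory threshold will be determined", and then "the vibrating intensity will be adjusted to either 60% of the sensory threshold or zero, depending on the group". The device sits on the wrist. Neither the side nor the site of threshold measurement is named.

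Blinding has two supports.

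- **Subject (Section D):** "Blinding to the light vibration stimulation is possible because subjects cannot perceive subthreshold (imperceptible) vibration". Section E.1.a, item 9 repeats this for sensation at the wrist: "Both groups will not feel any vibration at the wrist during therapy, because the vibration is either very small or none".
- **Therapist (Section D):** both groups are "supervised by the same therapist who is blinded to the group and does not know how the coin-sized device providing the light vibration works".

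The control condition is a silent device: "Group B will receive placebo, also in zero vibration at the wrist, during therapy" (Section E.1.a, item 9). Each subject has six two-hour sessions of hand and arm task practice. Nothing in the protocol text describes masking the device, limiting contact with it, or checking whether blinding held.

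**The concern.** The dose is scaled to the person who wears the device. It is therefore below threshold for that person, at the place and time of testing, and for nobody else by construction. The therapist supervises manual practice and may come into contact with the wrist; the subject has another hand. Neither is covered by the stated argument. Not being told the group, and not knowing how the device works, do not prevent someone from feeling it.

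Any direct detection would be one-sided, since a device set to zero gives nothing to feel. With one therapist for both groups, a therapist who has felt some devices could also learn from those that are silent.

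Two things depend on the blind holding: that both groups get equally intensive therapy, and that effort on timed dexterity tests and answers on the quality-of-life scales are not coloured by knowledge of the group. No planned data would show whether it held.

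**Working it through.** The documents give no vibration thresholds, so there is no plan figure to reproduce. The check is an inequality.

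**Inputs from the documents:** active level 0.6 × the subject's threshold, control level 0 (Section D); 30 subjects, 15 per group (Section E.1.a); 6 sessions each (Section D).

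**Step 1: condition for detection.** Let T_w be the wearer's threshold and T_o that of the touching hand. The touching hand can feel the device only if 0.6 × T_w > T_o, that is, T_w/T_o > 1/0.6 = 1.67. If the setting is an amplitude, this is 20 × log10(1.67) = 4.4 dB. The step assumes that the touching hand receives the same amplitude as the wrist skin, which the documents do not establish.

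**Step 2: assumed ratios (none is in the documents).**

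| T_w/T_o | Level relative to T_o | Above the touching hand's threshold? |
|---|---|---|
| 1.0 | 0.6 × 1.0 = 0.60 | no |
| 1.5 | 0.6 × 1.5 = 0.90 | no |
| 2 | 0.6 × 2 = 1.20 | yes |
| 3 | 0.6 × 3 = 1.80 | yes |

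In the control arm the level is 0 at any ratio.

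**Step 3: share of active subjects above the cut.** Assume that the ratio is lognormal with median m and log-SD s from 0.25 to 0.75. The share is p = 1 − Φ((ln 1.667 − ln m)/s), and the expected number is 15p.

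| Assumed median ratio | Share above 1.67 | Expected of 15 |
|---|---|---|
| 1.0 | 2% to 25% | 0.3 to 3.7 |
| 1.5 | 34% to 44% | 5.1 to 6.7 |
| 2 | 60% to 77% | 8.9 to 11.5 |
| 3 | 78% to 99% | 11.8 to 14.9 |

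The chance that at least one of 15 lies above the cut, 1 − (1 − p)^15, is 27% to 99% at median 1.0 and at least 99% from median 1.5. If every ratio were exactly 1.0, it would be zero. These are shares who *could* be detected, not shares who would be: contact with the running device is also needed.

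**Step 4: exposure.** 15 × 6 = 90 of the 30 × 6 = 180 sessions would have vibration on. This counts opportunities and says nothing about contact.

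**Step 5: context for bias, wholly assumed.** Suppose unblinding favoured vibration by 0.2 to 0.5 SD in half of the active arm. The mean shift is 0.5 × 0.2 = 0.10 to 0.5 × 0.5 = 0.25 SD. With SE = √(2/15) = 0.365 SD, a nominal two-sided 5% comparison of two means has type I error Φ(shift/SE − 1.96) + Φ(−shift/SE − 1.96) = 5.9% to 10.5%. This is a simple two-group approximation, not the planned repeated measures ANOVA.

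**The case against.** The physical premises are not in the documents. Sensory grading is by Semmes-Weinstein, which Sections C and E.1.a describe as a touch test on the fingertips; it is not a vibration threshold at the wrist. Entry is by motor score. No threshold is given for any wrist, unaffected hand or therapist. The therapist supervises practice in people with mild to moderate impairment, and handling an arm is not the same as touching a dime-sized device. All of this stands, and it is why the point is conditional.

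A reader might infer that stroke has raised the wrist threshold, so that the vibration will be felt by others. The documents do not support that: they name neither the side nor the test site, and ratios of 1.0 and 1.5 leave the stimulus below the other hand's threshold.

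A reader might also infer that one touch reveals the arm. That is too strong. The therapist is not told the group, and the documents do not say whether the therapist knows that one group is set to zero. Without that knowledge, feeling a vibration need not disclose the allocation.

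Finally, masking could itself interfere with the stimulus. The preliminary work taped the device to the skin, and a layer that damped it might change delivery. That objection shapes the fix. What it leaves untouched is the gap in the argument: imperceptible to the wearer is not the same as undetectable to others.

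**Conclusion.** The point holds in conditional form. The protocol secures imperceptibility for the wearer, at the site and time of threshold measurement. It does not show that the same level is undetectable to the therapist's hand or the subject's other hand. Detection needs both a threshold ratio above 1.67 and contact with the running device. With neither documented, the number of active subjects affected could be anywhere from none to most of the 15.

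It would be tempting to say that blinding fails in the vibration arm only. Direct detection is indeed possible only there, but with a shared therapist the consequences could reach the control arm, because a silent device would then carry information. Nor do the documents establish that blinding fails at all, or the direction and size of any bias; the type I error range above rests on assumed values.

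This is a possible one-sided route to unblinding in a trial that calls itself double-blind, worth closing because closing it is cheap.

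**What to change.** In Section D:

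1. Limit the imperceptibility claim to the wearer at the tested site, and do not offer it as the whole basis for blinding. Section E.1.a, item 9 already speaks only of sensation at the wrist.
2. In both arms, use an identical cover that does not press on or damp the device, and have it in place when the threshold is determined.
3. Instruct the therapist and the subject, in both arms, not to touch the device during sessions.

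Optionally, after the last session, record the subject's and the therapist's guess of the group, with a do-not-know choice, and report the answers descriptively by arm.

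The cost is a few sentences, a simple cover, brief training and some restriction on handling at the wrist; the optional guesses add two questions per subject. The stimulation level is unchanged.
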